16.8. Interim Analyses

Safety and PK data only will be reviewed by the IDMC after subjects in Cohort A have completed Week 12 Visit assessments, and before dosing any subjects in Cohort B.

After subjects in Cohort A complete the Week 24 Visit, [REDACTED], all available serum PK, [REDACTED] from [REDACTED] Cohort A will be analyzed by a statistical/PK team independent of the study. The grouped level summary statistics will be reviewed only by a limited number of individuals at Biogen who are not involved in the management of the subjects or subject-level data for the study. No changes to the study design are expected based on this review.

For the purpose of planning for future studies, an administrative interim analysis may be performed when approximately 60% of the subjects have completed the Week 52 Visit. A small unblinded team from Biogen, separate from the study management team, will have access to the unblinded interim analysis results.

A full analysis of the 1-year data will be performed after all subjects have completed the Week 52 Visit. A small unblinded team from Biogen, separate from the study management team, will have access to the unblinded 1-year analysis results.

An interim analysis when all subjects have completed the Week 72 Visit is planned to be conducted. A small unblinded team from Biogen, separate from the study management team, will have access to the unblinded interim analysis results.

A multiple comparison adjustment method will be applied to control the overall type I error at 0.05 in the study, due to the primary endpoint of change from baseline in MDS-UPDRS total score being analyzed at Week 52 and Week 72, and superiority against placebo is considered reached in the study if statistically significant result is achieved at either timepoint at the respective adjusted alpha-level. The details of the multiple comparison adjustment method will be pre-specified in the SAP. No additional multiplicity adjustments will be made for secondary or exploratory endpoint analyses.

CONFIDENTIAL

The information contained herein may not be used, disclosed, or published without the written consent of Biogen MA Inc.

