16.9. Sample Size Considerations

The sample size calculation is based on changes in MDS-UPDRS Part I + II + III total score at Week 52 and at Week 72 of treatment. Based on data from the Parkinson's Progression Markers Initiative study, the placebo subject's mean and standard deviation (SD) at Week 52 and Week 72 are assumed to be 8.0 (10.64) and 9.6 (13.7) respectively. Assuming a maximum of 55% reduction in the change from baseline in the active group with maximum response relative to placebo group, the mean (SD) for this active group will be 3.2 (10.64) and 3.84 (13.7) respectively at Week 52 and Week 72, and the responses for other active groups are assumed to be somewhere between 0 and the maximum response. The primary analysis will be based on the MCP-MOD method to detect a dose-response trend while controlling for multiplicity. Optimal contrasts will be constructed to detect potential dose-response trend under common dose-response curves (e.g., E_{\max} , exponential, logistic, linear in log dose, and quadratic model, which are illustrated with parameters shown in [Figure 5](#) which will be used for both Week 52 and Week 72). The planned enrollment is 311 subjects total (24 subjects in Cohort A and 287 subjects in Cohort B, [Table 8](#)). Actual enrollment is 357 subjects. In Cohort A, 29 subjects were randomized in a 1:1:1:1 ratio to each of the treatment groups, while in Cohort B 328 subjects were randomized in 2:1:2:2 ratio to the placebo, 250 mg, 1250 mg, and 3500 mg groups. Based on the actual enrollment, the estimated number of subjects by cohort and treatment groups are given in [Table 9](#) below. After accounting for dropout rate of 10% and 15% at Week 52 and Week 72, respectively, the estimated sample sizes are given in [Table 10](#) and [Table 11](#). With the updated sample size, the study will provide an average power of approximately 80% to detect the dose-response trend over 1 year of treatment, based on a 2-sided type I error of 0.05 and approximately 73% of power at the Week 72 analyses, based on a 2-sided type I error of 0.05. Overall, the sample size in the study will provide approximately 89% power. If there are any modifications to the candidate dose-response curves/models or parameters, the final candidate models for the MCP-MOD will be prespecified and described in the SAP.

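### Section 16.9 gives both primary-timepoint powers at the full two-sided 0.05, and an overall 89% with no alpha or correlation, although the two timepoints share one 0.05 with success at either

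*Protocol*

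**What the plan says.** Protocol Section 16.9 makes three power statements for the primary endpoint:

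- Week 52: "average power of approximately 80% to detect the dose-response trend over 1 year of treatment, based on a 2-sided type I error of 0.05".
- Week 72: "approximately 73% of power at the Week 72 analyses, based on a 2-sided type I error of 0.05".
- Both together: "Overall, the sample size in the study will provide approximately 89% power". No alpha, adjustment or between-timepoint correlation accompanies this figure.

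Section 16.8 sets the error budget: "A multiple comparison adjustment method will be applied to control the overall type I error at 0.05 in the study". It counts the study as positive if a "statistically significant result is achieved at either timepoint at the respective adjusted alpha-level". Sections 16.5.2.1 and 16.5.2.2 say the same for the Week 52 and Week 72 analyses. The method itself is deferred: "The details of the multiple comparison adjustment method will be pre-specified in the SAP".

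On effect size, the placebo changes (SDs) "are assumed to be 8.0 (10.64) and 9.6 (13.7) respectively" at Weeks 52 and 72. The best active group is described as having a 55% reduction, and its means are printed as 3.2 and 3.84.

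**The concern.** If a win at either timepoint is enough and the overall error is capped at 0.05, the two tests cannot both be run unconditionally at 0.05. At least one must use a smaller level, or a stepwise rule must apply. The 80% and 73% are labelled with the full 0.05 at each timepoint, so as labelled they belong to stand-alone tests and not to the planned procedure. The 89% has no label, and it has to be worked out which procedure it could belong to.

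This is the only power justification for the primary endpoint. It will also frame how a null result is read: a reader will take the chance of missing the assumed effect to be about 11%, and Week 52 power to be about 80%.

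**Working it through.** **Inputs.** From Section 16.9: 80% and 73% at two-sided 0.05; 89% overall; placebo mean (SD) 8.0 (10.64) and 9.6 (13.7); 55% stated reduction; active means 3.2 and 3.84. From Tables 10 and 11: placebo and 3500 mg sizes of 91 and 90 at Week 52, and 86 and 86 at Week 72. Assumed, because the Protocol does not give it: the correlation r between the Week 52 and Week 72 test statistics, taken over 0.3 to 0.8.

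**Step 1: reproduce the component powers.** Top dose against placebo with a 55% reduction:

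- Week 52: difference 8.0 × 0.55 = 4.40; standard error 10.64 × √(1/91 + 1/90) = 1.582; ratio 2.782; power Φ(2.782 − 1.960) = 79.4%.
- Week 72: difference 9.6 × 0.55 = 5.28; standard error 13.7 × √(2/86) = 2.089; ratio 2.527; power Φ(2.527 − 1.960) = 71.5%.

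Both are within 2 points of the printed values. Simulating the MCP-MOD test with assumed curve shapes (Figure 5 is not shown) gave 78–85% and 70–79% across shape sets; one set gave 81.4% and 73.4%. So 55% at a full 0.05 reproduces the components.

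**Step 2: reproduce the 89%.** Treat the two statistics as bivariate normal. With component powers p1 and p2, power at either timepoint is 1 − Φ₂(−z(p1), −z(p2); r). With p1 = 0.80 and p2 = 0.73 this equals 89.0% at r = 0.52. That is testing at 0.05 twice. Its two-sided study-wise error is 1 − P(|Z1| < 1.96 and |Z2| < 1.96) = 9.1% at r = 0.5, and 9.5% to 7.8% over r = 0.3 to 0.8.

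**Step 3: the same effects under error control.** The drifts are d1 = 1.960 + 0.842 = 2.802 and d2 = 1.960 + 0.613 = 2.573. At 0.025 each the critical value is 2.241, so Week 52 power is Φ(2.802 − 2.241) = 71.2% and Week 72 power is Φ(2.573 − 2.241) = 63.0%. Power at either timepoint:

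| r | 0.05 each (unadjusted) | 0.025 each | Hochberg | Equal alpha adjusted for r |
|---|---|---|---|---|
| 0.3 | 91.6% | 85.3% | 86.3% | 85.7% |
| 0.5 | 89.3% | 82.4% | 83.5% | 83.2% |
| 0.7 | 86.5% | 79.0% | 80.3% | 80.8% |
| 0.8 | 84.8% | 76.9% | 78.5% | 79.6% |

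From these drifts, 89% needs r of about 0.03 under the 0.025 split and about 0.1 under Hochberg. Neither is plausible for the same score in the same subjects 20 weeks apart.

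**Step 4: the effect-size conflict.** A 55% reduction gives active means of 8.0 × 0.45 = 3.60 and 9.6 × 0.45 = 4.32. The printed 3.2 and 3.84 are 8.0 × 0.40 and 9.6 × 0.40, a 60% reduction. Repeating Step 1 with 60%, the differences are 4.80 and 5.76 and the ratios 3.035 and 2.757:

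- at 0.05 each: 85.9% and 78.7%, which do not match 80% and 73%;
- at 0.025 each: 78.6% and 69.7%, with 89.1% at either timepoint for r = 0.4 and 87.8% for r = 0.5.

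One assumed MCP-MOD shape set with 60% at 0.025 each gave 81%, 72% and, at r = 0.5, 89% overall.

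**The case against.** The strongest reply is that the 89% has no stated alpha, so calling it unadjusted is inference. Step 4 gives that reply substance: with the printed means and a halved alpha, 89% is reachable at r of about 0.4 to 0.5 with study-wise error held at 0.05. This stands. A reader might infer that the 89% is simply wrong and that the chance of missing the assumed effect is clearly above 11%. The Protocol does not support that, because it leaves open which effect size, alpha and correlation produced the figure. For the same reason 71%, 63% and 77–85% are conditional values and not replacements to be printed. On this alternative reading, however, both 0.05 labels and the stated 55% are in error, so Section 16.9 still needs correcting.

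A second tempting inference is that the trial runs at 9% type I error. It does not. Sections 16.5.2.1, 16.5.2.2 and 16.8 commit to 0.05 overall, and Section 16.9 is a planning statement that authorises no test. The 9% belongs to the calculation that reproduces the 89%.

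Two further replies are fair. Deferring the multiplicity method to the SAP is acceptable and is not the fault raised here; but no later method lets both timepoints be tested unconditionally at 0.05 within a shared 0.05. And the 357 subjects are already enrolled, so the sample size does not move. That limits the consequence to how the study's power is stated and how its result is read.

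**Conclusion.** The inconsistency holds. As printed, the component powers use an alpha that the success rule does not allow for both tests, and the overall figure cannot be traced to an alpha or a correlation. There are two ways to read the section, and each leaves an error in it:

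- **80% and 73% at 0.05 are right (55% effect).** Then 89% matches unadjusted testing at r of about 0.5. Under an equal 0.025 split the figures are about 71% and 63%, with about 85% to 77% overall for r from 0.3 to 0.8. The chance of missing the assumed effect is then about 15% to 23%, against the 11% implied.
- **89% is right under error control.** Then the printed means (60% effect) and a reduced alpha were probably used, and the two 0.05 labels and the 55% are wrong.

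The first reading fits the component figures more closely, but the Protocol does not settle it. All the recalculated values rest on a normal approximation and an assumed correlation. The pairwise values also stand in for an average over candidate curves that are not shown.

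**What to change.** In Section 16.9:

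1. Reconcile the 55% reduction with the printed active means of 3.2 and 3.84, and state which was used.
2. State the alpha at each timepoint under the multiplicity method chosen for the SAP, in place of 0.05 at both.
3. State the assumed Week 52/Week 72 correlation and show overall power over a range around it.
4. Recompute and restate the Week 52, Week 72 and overall powers on that single basis. If about 80% is to be kept at Week 52 by giving it most of the 0.05, show the lower Week 72 power that results.

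The cost is one recalculation and a revised paragraph. Enrolment and study conduct do not change. The stated power may become less favourable.

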With an estimated sample size of 100 subjects dosed per arm in the 1250 mg and 3500 mg arms, the study has 80% probability of detecting AEs with a rate of 1.2% or greater in these 2 arms, and a 90% probability of detecting AEs occurring with a rate of 2.1% or greater.

CONFIDENTIAL

The information contained herein may not be used, disclosed, or published without the written consent of Biogen MA Inc.

Figure 5: Candidate Models for Dose-Response

[figure not shown]

Table 8: Estimated Sample Size Per Group (Planned)

	Treatment Group				Total
	Placebo	BIIB054 250 mg	BIIB054 1250 mg	BIIB054 3500 mg	
Cohort					
Cohort A	6	6	6	6	24
Cohort B	82	41	82	82	287
Total	88	47	88	88	311

CONFIDENTIAL

The information contained herein may not be used, disclosed, or published without the written consent of Biogen MA Inc.

Table 9: Estimated Sample Size Per Group Based on Actual Enrollment (Before Drop-Outs)

	Treatment Group				
	Placebo	BIIB054 250 mg	BIIB054 1250 mg	BIIB054 3500 mg	Total
Cohort					
Cohort A	8	7	7	7	29
Cohort B	93	47	94	94	328
Total	101	54	101	101	357

Table 10: Estimated Sample Size Per Group Based on Actual Enrollment (After Adjusting for 10% Drop-Out At Week 52)

	Treatment Group				
	Placebo	BIIB054 250 mg	BIIB054 1250 mg	BIIB054 3500 mg	Total
Cohort					
Cohort A	7	6	6	6	25
Cohort B	84	42	84	84	294
Total	91	48	90	90	319

Table 11: Estimated Sample Size Per Group Based on Actual Enrollment (After Adjusting for 15% Drop-Out At Week 72)

	Treatment Group				
	Placebo	BIIB054 250 mg	BIIB054 1250 mg	BIIB054 3500 mg	Total
Cohort					
Cohort A	7	6	6	6	25
Cohort B	79	40	80	80	279
Total	86	46	86	86	304

CONFIDENTIAL

The information contained herein may not be used, disclosed, or published without the written consent of Biogen MA Inc.

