
With a sample size of 88 subjects per arm in the 1250 mg and 3500 mg arms, the study has approximately 70% power to detect a 40% reduction in the active group relative to placebo in the change from baseline to Week 52 MDS-UPDRS total score, assuming the placebo mean change (SD) is 8.0 (10.64), based on the Parkinson's Progression Markers Initiative study data and a 2-sided alpha of 0.2.

With a sample size of 88 subjects per arm in the 1250 mg and 3500 mg arms, the study has 80% probability of detecting AEs with a rate of 1.8% or greater in these 2 arms, and a 90% probability of detecting AEs occurring with a rate of 2.6% or greater.

CONFIDENTIAL

The information contained herein may not be used, disclosed, or published without the written consent of Biogen MA Inc.

Figure 32: Response Shapes

[original figure replaced with the one below]

[figure not shown]

Table 5: Sample Size Before Adjusting for 15% Dropout Rate

Cohort	Treatment Group				Total
	Placebo	BIIB054 250 mg	BIIB054 1250 mg	BIIB054 3500 mg	
Cohort A	5	5	5	5	20
Cohort B	69	34	69	69	241
Total	74	39	74	74	261

Table 4 Table 6: Sample Size After Adjusting for 15% Dropout Rate

Dose	Treatment Group				Total
	Placebo	BIIB054 3 mg/kg 250 mg	BIIB054 15 mg/kg 1250 mg	BIIB054 45 mg/kg 3500 mg	
Cohort A	6	6	6	6	24
Cohort B	5282	2641	5282	5282	182287
Total	5888	3247	5888	5888	206311

CONFIDENTIAL

The information contained herein may not be used, disclosed, or published without the written consent of Biogen MA Inc.

Rationale: The number of subjects in the study was increased in order to allow enough power for statistical analyses based on DaT/SPECT with a shorter treatment duration. The updated response shape diagram (now Figure 3) and tables support the sample size calculations. Power to detect changes in MDS-UPDRS score and AE incidence has also been provided.

This change also affects Section 4.1, Study Schematic; Section 7.1, Study Overview; Section 9.2, Randomization and Registration of Subjects; and Section 11.1, Regimen.

To coordinate with this change, there was a corresponding increase in the number of study sites. The change in the number of study sites affects Section 7.1, Study Overview.

Section 8.1, Inclusion Criteria

Inclusion criterion 2:

Now reads:

2. Diagnosed with ~~idiopathic~~ PD **within the last a maximum of 5-3 years without motor fluctuations or dyskinesia prior to Screening.** Subjects must have:

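### The adverse-event detection limits given for 100 subjects per arm (1.2% at 80%, 2.1% at 90%) do not follow from 100 subjects; the limits are 1.6% and 2.3%

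*Protocol*

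**What the plan says.** Protocol Section 16.9 (Sample Size Considerations) closes its text with a statement on safety. It opens "With an estimated sample size of 100 subjects dosed per arm in the 1250 mg and 3500 mg arms" and continues that "the study has 80% probability of detecting AEs with a rate of 1.2% or greater in these 2 arms", and that there is "a 90% probability of detecting AEs occurring with a rate of 2.1% or greater". It does not define detection.

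Table 9 in the same section shows 101 subjects in each of the 1250 mg and 3500 mg arms before drop-out, so the rounded 100 agrees with actual enrollment.

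**The concern.** The sentence fixes a sample size, two probabilities and two rates, so it can be checked directly. At 100 subjects per arm, the rate detectable with 80% probability should be about one third higher than the one printed (1.6% against 1.2%), and the 90% rate should also be higher (2.3% against 2.1%).

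Dose-related safety is the first secondary objective in Section 6, and Section 16.1.2 plans mainly descriptive summaries. This sentence is the only precision that the protocol states for safety. A reader who relies on it would think that each higher-dose arm is more likely to reveal an uncommon event than it is.

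**Working it through.** **Inputs**

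- Subjects dosed per arm: n = 100 (Section 16.9); 101 in Table 9.
- Stated limits: 1.2% at 80% and 2.1% at 90% (Section 16.9).
- Drop-out-adjusted sizes of these arms: 90 at Week 52 (Table 10) and 86 at Week 72 (Table 11).

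**Formula.** Detection is taken as at least one event in n independent subjects with true rate p:

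P = 1 − (1 − p)^n, so the rate detectable with probability P is p = 1 − (1 − P)^(1/n).

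**Is this the method behind the sentence?** The Version 2 amendment summary, appended to the protocol, has the same statement for 88 subjects per arm: "the study has 80% probability of detecting AEs with a rate of 1.8% or greater in these 2 arms", with 2.6% for 90%. That text is superseded and is used here only to identify the method. At n = 88:

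- 1 − 0.2^(1/88) = 1.81%, printed as 1.8%
- 1 − 0.1^(1/88) = 2.58%, printed as 2.6%

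Both match after rounding, so the formula is the plan's own.

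**Current figures at n = 100**

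- 80%: 1 − 0.2^(1/100) = 1.60%, where the protocol prints 1.2%
- 90%: 1 − 0.1^(1/100) = 2.28%, where the protocol prints 2.1%
- Probability of seeing a 1.2% event: 1 − 0.988^100 = 70.1%, not 80%
- Probability of seeing a 2.1% event: 1 − 0.979^100 = 88.0%, not 90%

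Rounding does not explain the gap. Taking the printed rates at the top of their rounding range (1.249% and 2.149%) gives 71.5% and 88.6%.

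**Sample size implied by each printed rate**

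- 1.2% at 80%: ln 0.2 / ln 0.988 = 133.3, so 134 subjects
- 2.1% at 90%: ln 0.1 / ln 0.979 = 108.5, so 109 subjects

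The two differ, so no single n gives both rates as limits.

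**Other readings**

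| Reading | Probability at 1.2% (stated 80%) | Probability at 2.1% (stated 90%) |
|---|---|---|
| At least 1 event, n = 101 (Table 9) | 70.5% | 88.3% |
| At least 1 event, n = 90 (Table 10) | 66.3% | 85.2% |
| At least 1 event, n = 86 (Table 11) | 64.6% | 83.9% |
| Two arms pooled, n = 200 | 91.1% | 98.6% |
| At least 1 event in each of two arms of 100 | 49.1% | 77.5% |
| At least 2 events, n = 100 | 33.8% | 62.3% |
| At least 2 events, n = 200 | 69.3% | 92.4% |
| Poisson approximation, n = 100 | 69.9% | 87.8% |

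None gives 80% and 90% together. For the pooled arms the limits at n = 200 would be 0.80% and 1.14%.

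**The case against.** The strongest alternative concerns the denominator. Section 9.2 re-randomizes Year 1 placebo subjects in equal ratio to the three active doses for Year 2. With 101 placebo subjects, about 34 would join each higher-dose arm, giving 101 + 34 = 135 ever exposed per arm before drop-out. At n = 135 the 80% limit is 1 − 0.2^(1/135) = 1.19%, which is the printed 1.2%. Section 16.1.2 does plan summaries of overall experience on BIIB054, so this denominator is not far-fetched.

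It still does not rescue the sentence. The stated n is 100, and Section 16.1.2 makes Year 1 the primary safety evaluation. At n = 135 the 90% limit would be 1.7%, not 2.1%. A 2.1% event would then be seen with probability 94%, so the second statement would hold only as a loose lower bound. The point does show that the faulty element could be n, or a mix of two denominators, and not the rates alone.

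Three points on weight stand:

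- The second figure is a small error, about 2 percentage points of probability.
- The sentence is a prospective detection probability, not an upper confidence bound, and the protocol ties no monitoring-committee action or stopping rule to it.
- Enrollment is complete, and the sample size rests on the MDS-UPDRS, so nothing in the design changes.

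**Conclusion.** The statement is wrong as written. With 100 subjects per arm the detection limits are 1.6% at 80% and 2.3% at 90%. The material error is the first: the protocol claims an 80% chance of seeing a 1.2% event where the design gives 70%, so the chance of missing it in an arm is half as large again as stated (30% against 20%). Both errors run in the favorable direction.

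This assumes that detection means at least one event in an arm, with independent subjects and a common rate. The protocol does not define the term, but this meaning reproduces the sponsor's own figures for 88 subjects, and no alternative tried gives both current figures. The consequence is confined to a descriptive statement of safety sensitivity, which should be corrected.

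**What to change.** In Section 16.9, keep 100 subjects per arm and replace the rates with 1.6% (80%) and 2.3% (90%). State that detection means at least one event within an arm. As a check, at n = 100 a 1.6% rate gives 80.1% and a 2.3% rate gives 90.2%.

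If the two arms together are meant, say so and print 0.8% and 1.1% for 200 subjects. If another denominator was intended, such as all subjects ever exposed to a dose, state that n and derive both rates from it.

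The cost is two numbers and a short definition in one sentence. The stated safety sensitivity becomes slightly less favorable; no analysis, sample size or procedure changes.

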17. ETHICAL REQUIREMENTS

Biogen, [REDACTED] and the Investigator must comply with all instructions, regulations, and agreements in this protocol and applicable International Council for Harmonisation (ICH) and Good Clinical Practice (GCP) guidelines and conduct the study according to local regulations.

The Investigator is responsible for endorsing all data on completed eCRFs via signature prior to any interim lock or database lock.

The Investigator may delegate responsibilities for study-related tasks where appropriate to individuals sufficiently qualified by education, training, and experience, in accordance with applicable ICH and GCP guidelines. The Investigator should maintain a list of the appropriately qualified persons to whom significant study-related duties have been delegated. The Investigator is responsible for supervising those individuals and for implementing procedures to ensure the integrity of the tasks performed and any data generated.

